9.7.2.5 Sensitivity Analysis

Selected sensitivity analyses may be performed to assess the impact of using other analysis sets if appropriate.

9.7.2.5.1 Subgroup Analysis

Subgroup analysis may be used to investigate the covariates listed in section 9.3.3. If there is insufficient number of subjects in each level of a subgroup (eg, < 10 subjects), then the subgroup analysis will not be performed.

Date: 29 April 2019 Page 38 of 64

9.7.3 Analysis of Safety Outcomes

Number of subjects with serious and non-serious ADRs leading to discontinuation of panitumumab and serious ADRs associated with fatal outcomes will be tabulated by system organ class and preferred term.

Measures of skin toxicity management (FACT- EGFRI-18 QoL questionnaire (See Appendix F) if allowed per local regulations), type of measures, duration, severity of skin toxicity, and type of treatment will be summarized.

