Skin reactions are a pharmacological effect of EGFR inhibitors application. Injectable EGFR inhibitors rarely cause systemic toxicities generally associated with chemotherapy. However, these injectable anti-EGFR agents are associated with mild skin toxicities in more than 60—90% of subjects (Leporini, 2013; Melosky, 2009; Bonner, 2010: Velenik, 2010: Kim, 2016). These skin toxicities represent the most common adverse drug reactions caused by the injectable EGFR inhibitors (Kubo, 2016; Takahashi, 2015; Mittmann and Seung, 2011; Fabbrocini, 2015). In subjects treated with cetuximab and panitumumab, approximately 80% and 86%, respectively, experience a skin toxicity, the majority of which are mild (Velenik, 2010; Kim, 2016; Bonner, 2010). Severe grade skin toxicities, (grade 3 - 4), occur in only 5-18% of subjects treated with cetuximab and 14% in those treated with panitumumab (Abdullah, 2012). Safety analysis of PRIME study revealed skin toxicity in 38% of panitumumab+ FOLFOX4-treated and 2% of FOLFOX4-treated subjects.

According to the European SmPC (summary of product characteristics), the first symptom of a dermatological reaction is observed in median time of 10 days, and the median time to resolution of such a reaction after the last dose of panitumumab is 28 days.

Skin toxicities can have a profound impact on subject quality of life due to symptoms caused and potential aesthetic consequences. Furthermore, inappropriate management of skin toxicities can increase the risk of dose reduction, discontinuation or withholding of the cancer treatment (Boone, 2007). However, no significant differences in quality of life measured every 4 weeks between subjects with grade 0–2 skin toxicity and those with grade 3+ skin toxicity were reported in PRIME study (Siena, 2016).

In recent years, clinical guidelines recommend that prophylactic measures are the preferred option to managing acute skin reactions. Appropriate prophylactic measures can effectively reduce the severity (although perhaps not incidence) of skin reactions in subjects treated with injectable EGFR inhibitors and have therefore the potential to directly benefit subjects (Bonner, 2010; Melosky, 2009; Abdullah, 2012).

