9.2.8 Safety Follow-up

Safety follow-up will last approximately 30 days after the start of 2nd line treatment, or after 15 months of observation if panitumumab was administered in the last 4 weeks of observation, whichever occurs first, except for death, withdrawal of consent or lost to follow-up.

Date: 29 April 2019 Page 30 of 64

The following data, at the End of Observation Visit will be collected where available and recorded as standard clinical practice:

- Adverse Events: type and duration of AE incident; occurrence of skin toxicity and details of skin toxicity management using FACT- EGFRI-18 QoL questionnaire (See Appendix F) if permitted in a country per local regulations.
- All other safety events with the exception of the protocol exempted events.
- Concomitant medications
- Laboratory values: haematology and chemistry
- Tumour evaluations:
 - evaluation and re evaluation / assessment (methods, criteria, timing Q2M), RECIST criteria (if available)
 - ETS at week 8 (if available) measured using all or any of the following methods: CT, MRI, PET
 - disease evaluation as routinely monitored (if different than RECIST criteria), including chest X rays, bone X rays, ultrasound assessments (any performed) or radionuclear examinations
 - information about biomarker status (if available).

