9.3.2 Outcome Assessment

Primary outcomes

As primary outcomes the following data will be collected:

- characteristics of subjects with WT RAS non resectable mCRC receiving panitumumab in combination with chemotherapy as a 1st line treatment, including:
 - demographics: age, sex
 - targeted medical history: type of primary tumour and the date of diagnosis; site of primary tumour: rectum vs colon, right vs left colon; surgical procedures; lymph nodes: number and involvement; TNM stage; adjuvant chemotherapy, including regimen if applicable; sites of metastatic disease: liver, lung, other;
 - current status of mCRC: ECOG performance status, RECIST criteria (if available), ETS at week 8 (if available)
- pattern of treatment composed of:
 - 1st line treatment: agents and doses at baseline, any changes during
 1st line treatment, including dose, infusion schedule, and reasons for changes
 - 2nd line treatment: type of progression leading to 2nd line choice, type of 2nd line anti-cancer therapy, dose, schedule and reason for treatment selection

Secondary outcomes

In the secondary outcomes the following data will be gathered:

- Response to 1st line treatment measured as:
 - Death
 - Disease Progression
 - response rate (RR)
 - rate of conversion to resectable mCRC
 - tumour markers: CEA and CA 19.9
 - ETS (if available as per clinical practice) at week 8 measured by all or any of the following methods: CT, MRI, PET in comparison to the baseline.
- Safety assessments:
 - ADR reports related to panitumumab treatment
 - type and duration of ADR incident

Exploratory outcome

CCI

Date: 29 April 2019 Page 32 of 64

In study sites routinely performing biomarkers assessment in liquid biopsies, disease biomarkers information will be collected as per local regulations.

Since this is an observational study, all tests will be performed in line with routine clinical practice and no additional procedures are posed by the protocol.

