9.7.2.2 Missing or Incomplete Data and Lost to Follow-up

All available data collected during the retrospective and prospective observation periods, the safety follow-up period, and the end of study visit will be used in the analysis. The eCRFs will be designed to minimise missing data and to optimise the integrity of collected data. Subjects' records will not be excluded because of missing data and missing data will not be inputted. For categorical variables, missing responses will be shown as a separate category in the analysis. For numeric variables, the number of non-missing observations will be presented.

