Appendix E. Schedule of Assessments

Data to be collected	Baselinea	Observation Period									
		Monthly follow-up dateb	Safety follow up ^o	End of Study							
Enrollment	x										
Demographics	x										
Targeted medical history	×										
Physical measurement	x	x									
Vital Signs	x	x									
Events (Observational study)		x	х	x							
Concomitant medications	x	x	х	х							
1st line of treatment	×	x									
2 nd line of treatment		x									
Panitumumab administration	x	x									
Substance use	x										
Laboratories	x	x	х								
Reproductive status	x										
ECOG performance status	x	x									
Disease history	x										
Tumor evaluations	x	x	х								
Site characteristics	×										

^aBaseline will be from 1 to maximum 12 months preceding enrolment in the study

[figure not shown]

Data will be collected for 15 months

[°]This is 30 days after the end of 1st line of treatment

Date: 29 April 2019 Page 62 of 64

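### Duration of ADRs and skin toxicity is to be summarised on non-missing values, with no rule for reactions still unresolved at last contact

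*Protocol*

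**What the plan says.** Section 9.3.2 lists "type and duration of ADR incident" among the secondary safety outcomes, and Table 2 repeats it, by country and in total. For skin toxicity, Section 9.7.3 states that "type of measures, duration, severity of skin toxicity, and type of treatment will be summarized".

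Three general rules bear on how that summary is made. Section 9.7.2.1 describes continuous outcomes by the number of non-missing values, mean, standard deviation, median, quartiles and range. Section 9.7.2.2 rules out imputation and adds: "For numeric variables, the number of non-missing observations will be presented". Section 9.7.2.1 also assigns the Kaplan-Meier estimator to time-to-event data in general. Section 9.7.2.4 names that estimator for death and disease progression; no section names it for the duration of a reaction.

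On the time scale, Section 7.1 reports from the product information that "the median time to resolution of such a reaction after the last dose of panitumumab is 28 days". Section 9.2.8 says: "Safety follow-up will last approximately 30 days after the start of 2nd line treatment". It gives month 15 as the other starting point, for subjects dosed with panitumumab within the preceding 4 weeks. The footnote to Appendix E starts the clock elsewhere: "This is 30 days after the end of 1st line of treatment". Section 11.1.1 requires no adverse event monitoring after end of study.

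**The concern.** Duration can be computed only when both onset and end are known. The adverse event form instructions in Appendix B pair an unresolved event with an unknown end date. If duration is handled as an ordinary numeric variable, as the word summarised together with Sections 9.7.2.1 and 9.7.2.2 suggests, every reaction still open at last contact leaves the calculation. Those are not a random subset: among reactions open at the last dose, the ones that outlast the contact window are the slow ones. Section 9.9.4 points the same way by allowing incomplete data to be excluded.

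The follow-up window is close to the protocol's own median time to resolution, so the loss need not be small. Section 7.2 makes the impact and management of skin toxicity, for the use of payers, an explicit aim. A resolved-only duration would be a poor basis for that.

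**Working it through.** The plan computes no figure for duration, so there is none to reproduce. The check asks what share of durations the stated rules would lose.

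**Inputs**
- Median time from last dose to resolution: 28 days (Section 7.1).
- Post-dose contact W. W = 30 days if the clock starts at the end of 1st line and that coincides with the last dose (Appendix E). W = 28 + 30 = 58 days if the subject reaches month 15 with the last dose 4 weeks earlier (Section 9.2.8).
- Shape of the resolution time: not given. Exponential is assumed as the main case, Weibull shapes 0.7 to 2 as the range.
- Share s of all skin reactions still ongoing at the last dose: not given; 25% to 100% assumed.

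**Share unresolved among reactions ongoing at the last dose** (exponential): S(W) = 0.5^(W/28).
- S(30) = 0.5^(30/28) = 47.6%
- S(58) = 0.5^(58/28) = 23.8%

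**Median post-dose time among resolved reactions only**: m = −(28/ln 2) · ln[1 − (1 − S(W))/2].
- W = 30: m = −40.4 · ln(1 − 0.262) = 12.3 days, against 28
- W = 58: m = −40.4 · ln(1 − 0.381) = 19.4 days, against 28

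**Sensitivity to shape**, S(W) = exp[−ln 2 · (W/28)^k]:

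| Weibull shape k | Unresolved, 30 d | Resolved-only median, 30 d | Unresolved, 58 d | Resolved-only median, 58 d |
|---|---|---|---|---|
| 0.7 | 48.3% | 8.4 d | 31.5% | 13.6 d |
| 1 | 47.6% | 12.3 d | 23.8% | 19.4 d |
| 1.5 | 46.4% | 16.5 d | 12.7% | 24.7 d |
| 2 | 45.1% | 19.0 d | 5.1% | 27.0 d |

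At 30 days the share lost hardly depends on the shape, because 30 is so near the median. At 58 days it depends on it strongly.

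**Share of all reactions lost**: s · S(W), exponential.
- s = 25%: 11.9% at 30 days, 5.9% at 58 days
- s = 50%: 23.8% and 11.9%
- s = 100%: 47.6% and 23.8%

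**Effect on total duration.** The 28 days run from the last dose, not from onset. If every reaction had already lasted D days at the last dose, the 30-day window would turn a median of D + 28 into D + 12.3. For D = 60 that is 72.3 instead of 88 days; for D = 150, 162.3 instead of 178. The absolute loss is 28 − 12.3 = 15.7 days throughout, and the relative loss shrinks as D grows.

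**The other end of the interval.** Section 7.1 says "the first symptom of a dermatological reaction is observed in median time of 10 days", whereas enrolment is at least 1 month after the first infusion (Section 9.2.3.1) and safety data are not collected retrospectively (Section 9.2.5). At least half of first skin reactions therefore begin before a subject can be enrolled. Those seen prospectively are the ones that have lasted until consent, which favours long reactions.

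**The case against.** The strongest reply is that this belongs to the statistical analysis plan. Section 9.7.1 defers details there, the protocol nowhere says that unresolved reactions are dropped, and a plan that treated duration as time-to-event data would comply fully with Section 9.7.2.1. That stands in part: exclusion is inferred from the general rules, not stated for ADRs, and nothing in the protocol blocks the better method. But the protocol is not merely silent. It fixes a non-missing, no-imputation rule and describes duration in the language of descriptive statistics; followed as written, that produces the truncated figure.

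Three stronger readings are tempting and not supported.
- A reader might infer that half of all skin reactions persist 28 days after the last dose. The figure can apply only to reactions present at that dose; those that resolve on treatment are unaffected.
- A reader might infer that Kaplan-Meier is reserved for death and progression. The general sentence in Section 9.7.2.1 is not so restricted; duration is simply not placed under it.
- A reader might infer that subgroups become non-comparable because subjects who stop 1st line without a 2nd line can be observed longer. Table 2 plans ADR summaries by country and in total only, and no comparison by reason for leaving observation is planned.

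It is also fair to say that 30 days is near the unfavourable end for subjects who complete follow-up. Under Section 9.2.8 any gap between the last dose and the start of 2nd line adds to the window, and 58 days is no upper limit for those subjects. Subjects who die, withdraw or are lost may have less. Finally, the selection of long reactions at enrolment works against the loss of long reactions at the end, so the net direction of bias over all reported durations is not established.

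**Conclusion.** The point holds in a limited form. Duration is a stated outcome, the general rules leave reactions unresolved at last contact without a value, and no rule is given for them. Taken alone, that loss shortens the reported duration. Among reactions ongoing at the last dose, about 48% would be lost with 30 days of contact (45% to 48% over the shapes tried) and about 24% with 58 days (5% to 31%). These figures rest on the protocol's 28-day median and an assumed distribution. The share of all reactions affected is smaller unless every reaction is ongoing at the last dose, and cannot be taken from the document. It also depends on the start of Safety Follow-up, where Section 9.2.8 and Appendix E disagree and must be reconciled. The primary objective is untouched. What is affected is a secondary safety outcome and the skin-toxicity description meant for payers.

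**What to change.** In Section 9.7.3:
- Declare the duration of ADRs and of skin toxicity to be time-to-event data under Section 9.7.2.1, estimated by Kaplan-Meier.
- Censor unresolved reactions at the date of last contact. The End of Study Visit alone will not serve, since subjects who die, withdraw or are lost may not have one.
- Report the number of reactions unresolved, and do not present the duration of resolved reactions on its own.
- Either restrict the estimate to reactions with onset after consent, or use delayed entry for those already present at enrolment. Delayed entry needs an onset date from the medical history; restriction is simpler but leaves out many reactions.
- State how death with an ongoing reaction is handled.

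Separately, reconcile the start of the 30 days between Section 9.2.8 and Appendix E.

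The cost is a few sentences and slightly more analysis work. The sample form in Appendix B already has end date and resolved or not-resolved status, and Section 9.2.9 already collects safety events, so no visit is added. The downside is that some medians will be longer or not estimable: with 30 days of contact, a 28-day post-dose median lies only just inside the window.

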9.8 Quality Control

The overall procedures for quality assurance of clinical study data are described in the Amgen Standard Operational Procedures. In short, data quality and integrity will be assured by verification and cross-check of the eCRFs against the investigator's records by the study monitor. The data in the eCRF will be verified electronically. Discrepancy reports will be generated and transferred to the site for resolution of the Investigator.

9.9 Limitations of the Research Methods

Potential limitations of the study design relate to the ability to include a sufficient sample of subjects meeting the eligibility criteria, namely having non resectable wild type *RAS* mCRC and receiving panitumumab in combination with chemotherapy as 1st line treatment. To minimize the risk, the study will include a sufficient number of centres to be able to capture an adequate study population that represents subjects treated with panitumumab. The results gathered in central and eastern European (CEE) countries may be generalized, especially for countries having similar health care systems.

Data sources limitation is expected to be low due to the mainly prospective design of the study. In case of unexpected or incorrect data, clarifications will be sought based on medical records. Any inconsistencies will be reviewed and resolved during frequent data extractions.

9.9.1 Internal Validity of Study Design

9.9.1.1 Selection Bias

There are 3 major areas of potential selection bias for the study. Firstly, recruited subjects should have metastatic stage of the disease and should receive at least one infusion of panitumumab in combination with chemotherapy prior to enrolment. There might be a small group of subjects who cease treatment after first dose, usually because of death or disease progression. The survival bias may be slightly inflated and impact other collected data. However, due to the prospective design of the study, subjects will

Date: 29 April 2019 Page 39 of 64

be alive at enrolment. For deceased subjects, the Safety Follow-up data will be impossible to obtain. The nature of an observational study involves some difficulties in obtaining data, therefore the bias of missing data is anticipated.

Lastly, subject selection may depend to a certain extend on the reimbursement which differs per country. Because of financial burden of treatment a more wealthy subject population may be enrolled that does not represent the selected countries population of subjects with mCRC. Different reimbursement policies may result in differences in subject characteristics in each country.

9.9.1.2 Confounding

Any confounding factors, such as demographic (eg, age, gender, country) or clinical characteristics (eg, primary tumour location, oxaliplatin-based chemotherapy for mCRC, irinotecan-based chemotherapy for mCRC) have been considered and the effort will be made to complement them during the study. For data analysis, the confounding factors will be controlled.

9.9.2 External Validity of Study Design

The planned selection of the study population assumes the inclusion of subjects who are currently treated with panitumumab in combination with chemotherapy.

Study population may depend on the type of recruitment centre. To avoid centre selection bias, two approaches are planned: to include a wide range of hospital types covering the entire area of the country and to review the data extractions frequently.

9.9.3 Analysis Limitations

The analysis could be limited by the availability of genetic data, like *RAS* status and other important biomarkers that are tested in centres with routine practice of liquid biopsy only.

9.9.4 Limitations Due to Missing Data and/or Incomplete Data

As the study design is mainly prospective, this will minimize missing data. There is a risk that there will be some incomplete data and it will not be possible to go back to the medical records to complete it adequately so incomplete data may need to be excluded from the analysis. We will be performing frequent data extractions to review any inconsistencies within the data.

10. Protection of Human Subjects

The study will comply with all the local applicable laws, regulations, and guidance regarding human subject protection. For more details, see Appendix A.4.

Date: 29 April 2019 Page 40 of 64

10.1 Informed Consent

An Informed Consent Form must be signed by the subject before enrolling in the study as per local regulations.

Before the subject medical chart may be used, the participating physician is responsible for obtaining written ICF from the subject, in order to have permission to use the necessary data, if applicable.

The acquisition of ICF should be documented in the subject's medical records, and the ICF should be signed and personally dated by the subject and by the person who

conducted the informed consent discussion. The original signed ICF should be retained in accordance with institutional policy, and a copy of the signed consent and assent form should be provided to the subject.

10.2 Independent Ethics Committee (IEC)

The study will be conducted in accordance with country specific legal and regulatory requirements, as well as with scientific purpose, value and rigor and follow generally accepted research practices described in Good Epidemiological Practice (GEP) guidelines issued by the International Epidemiological Association (IEA).

All data will be handled in the strictest confidence in conformity with national and European data protection regulations (such as Directive 95/46/EC).

A copy of the protocol, and all other documents as per local regulation, must be submitted to the Ethics Committee and Regulatory Agency for written approval. A copy of the written approval of the protocol must be received by Amgen before the study can be executed.

The Sponsor must submit and obtain approval from the Ethics Committee and Regulatory Agency for all subsequent protocol amendments.

10.3 Subject Confidentiality

The Investigator must ensure that the subject's confidentiality is maintained:

- On the CRFs or other documents submitted to Amgen, subjects should be identified by a subject identification number only, with age and/or year of birth on the demographics CRF.
- For ADRs, SADRs, product complaints and other reportable safety events reported to Amgen, subjects should be identified by their, age and/or year of birth and a subject identification number.
- Documents that are not for submission to Amgen (eg, signed informed consent forms) should be kept in strict confidence by the Investigator.

Date: 29 April 2019 Page 41 of 64

In compliance with local regulations, it is required that the Investigator and institution permit authorized representatives of the company, of the regulatory agency(s), and the IEC direct access to review the subject's original medical records for verification of study-related data. Direct access includes examining, analysing, verifying, and reproducing any records and reports that are important to the evaluation of the study. The Investigator is obligated to inform and obtain the consent of the subject to permit named representatives to have access to his/her study-related records, including personal information, without violating the confidentiality of the subject.

